3.6. Safety Endpoints

Safety will be assessed by the spontaneous reporting of adverse events (AEs), physical examinations and clinical laboratory results in all subjects who receive at least one dose of the investigational product. Unscheduled safety assessments may be performed at any time during the study to assess any perceived safety concerns.

There will be two sets of safety summary tables:

- PF-06650833 (400, 200, 60, 20 mg, QD) and placebo.

090177e190fc4501Approved\Approved On: 27-May-2019 06:05 (GMT)

- PF-06650833 (400, 200, 60, 20 mg, QD), tofacitinib, and placebo.

3.6.1. Adverse Events

An adverse event is considered treatment emergent relative to a given treatment if:

- The event occurs for the first time during the effective duration of treatment and was not seen prior to the start of treatment (for example, during the baseline or run-in period), or
- The event was seen prior to the start of treatment but increased in severity during treatment.

A 3-tier approach will be used to summarize AEs. Under this approach, AEs are classified into 1 of 3 tiers. Different analyses will be performed for different tiers (see [Section 6.7.1](#)).

Tier-1 events: These are pre-specified events of clinical importance and are maintained in a list in the product's Safety Review Plan.

Tier-2 events: These are events that are not tier-1 but are "common". A Medical Dictionary for Regulatory Activities (MedDRA) Preferred Term (PT) is defined as a tier-2 event if there are at least 4 in any treatment group.

Tier-3 events: These are events that are neither tier-1 nor tier-2 events.

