6.7. Safety Summaries and Analyses

Safety analysis will be based on the SAF analysis set. The summary will be done for:

- PF-06650833 (400, 200, 60, 20 mg, QD) and placebo;
- PF-06650833 (400, 200, 60, 20 mg, QD), tofacitinib, and placebo.

All clinical AEs, serious adverse events (SAEs), treatment-emergent signs and symptoms (TEAEs), withdrawal due to AEs, ECGs, vital signs and safety laboratory data will be reviewed and summarized on an ongoing basis during the study to evaluate the safety of subjects.

Safety data will be presented in tabular and/or graphical format and summarized descriptively, where appropriate. All safety endpoints will be listed and summarized in accordance with Pfizer Data Standards. Categorical outcomes (eg, AEs) will be summarized by subject counts and percentage. Continuous outcome (eg, blood pressure, pulse rate, etc) will be summarized using N, mean, median, standard deviation, etc. Change from baseline in laboratory data, ECGs and vital signs will also be summarized. Subject listings will be produced for these safety endpoints accordingly.

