6.7.1. Adverse Events

It should be recognized that most studies are not designed to reliably demonstrate a causal relationship between the use of a pharmaceutical product and an adverse event or a group of adverse events. Except for select events in unique situations, studies do not employ formal adjudication procedures for the purpose of event classification. CCI

[REDACTED]

[REDACTED]

Nominal p-values (Tier-1 events only) and 95% confidence intervals (Tier-1 and Tier-2 events) will be provided for between treatment differences in the percentage of patients with events. Reporting p-values and confidence intervals will follow Pfizer standards.

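### The tier-2 adverse event threshold is counted arm by arm and no combined PF-06650833 group is listed, so an event spread evenly over the four doses can miss a planned drug-versus-placebo interval

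*SAP*

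**What the plan says.** SAP 3.6.1 sorts adverse events into three tiers.

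- **Tier 1:** "These are pre-specified events of clinical importance and are maintained in a list in the product's Safety Review Plan". No count is required.
- **Tier 2:** common events outside tier 1. A Preferred Term "is defined as a tier-2 event if there are at least 4 in any treatment group". The unit of the 4 is not printed; subjects is the natural reading.
- **Tier 3:** "These are events that are neither tier-1 nor tier-2 events".

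SAP 6.7.1 ties the inferential output to the tiers: "95% confidence intervals (Tier-1 and Tier-2 events) will be provided for between treatment differences in the percentage of patients with events". Nominal p-values go to tier 1 only.

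SAP 3.6 and 6.7 name two sets of safety tables. The groups are "PF-06650833 (400, 200, 60, 20 mg, QD) and placebo" in the first and "PF-06650833 (400, 200, 60, 20 mg, QD), tofacitinib, and placebo" in the second. Neither list names a combined PF-06650833 group. Whatever the tier, "Categorical outcomes (eg, AEs) will be summarized by subject counts and percentage".

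**The concern.** The drug is divided over four small arms and the tier-2 count is taken within each arm. A side effect that occurs at a similar rate at every dose is thus judged four times on a quarter of the data and never once on all of it. If no arm reaches 4, the event falls to tier 3 and the plan provides neither a difference from placebo nor an interval.

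This is the first study of the drug in RA (protocol 1.8), and safety is the first-listed secondary objective. A flat dose pattern is plausible on the sponsor's own account: protocol 1.4 reports no clear link between dose and adverse event incidence or severity in the Phase 1 studies. The most precise drug-versus-placebo comparison the trial can give is the pooled one, and the visible plan does not ask for it, even for events that do reach tier 2.

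**Working it through.** **Arm sizes.** Protocol 9.1 gives 36 + 36 + 36 + 30 + 30 + 30 = 198 completers and about 230 enrolled at 15% dropout. Check: 198/(1 − 0.15) = 233 and 198 × 1.15 = 228, so 230 is reproduced closely enough. The safety set is everyone dosed, so randomised numbers are the right denominators. The 6:6:6:5:5:5 ratio (protocol 3) sums to 33, giving 230 × 6/33 = 41.8 and 230 × 5/33 = 34.8. I use 42/42/42/35 on PF-06650833 (161 in all) and 35 on placebo. These are pro rata assumptions.

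**What the threshold means.** Four subjects are 4/42 = 9.5% or 4/35 = 11.4% of a dose arm, but 4/161 = 2.5% of everyone on drug.

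**Chance that no dose arm reaches 4, given k cases on drug at equal rates.** Sum over all splits (a, b, c, d) with a + b + c + d = k and each at most 3:

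C(42,a) × C(42,b) × C(42,c) × C(35,d) / C(161,k)

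| Cases on drug (k) | Share of 161 | No dose arm reaches 4 |
|---|---|---|
| 6 | 3.7% | 86% |
| 8 | 5.0% | 57% |
| 10 | 6.2% | 22% |
| 12 | 7.5% | 2.4% |
| 13 or more | 8.1% or more | 0% |

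For k = 12 only the 3-3-3-3 split qualifies: 11480³ × 6545 / C(161,12) = 0.024. From 13 cases on, at least one arm must hold 4. Completer sizes (36/36/36/30) give almost the same answers: 57% at 8 cases and 2.4% at 12.

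**By true rate.** The chance that at least one dose arm reaches 4 is 1 − Π P(X ≤ 3), with X binomial in each arm:

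| True rate at every dose | Some dose arm has 4 or more | Combined group has 4 or more |
|---|---|---|
| 3% | 12% | 71% |
| 4% | 28% | 89% |
| 5% | 46% | 96% |
| 7.5% | 83% | over 99% |
| 10% | 97% | over 99% |

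The true rates are assumptions, shown as a range. Neither table counts triggers through placebo or tofacitinib.

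**Precision.** For a 10% event in both groups, the standard error of drug minus placebo is:

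- one 42-subject dose arm: √(0.09 × (1/42 + 1/35)) = 6.9 points;
- all doses pooled: √(0.09 × (1/161 + 1/35)) = 5.6 points, about 19% smaller.

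**The case against.** Four objections carry weight.

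*Nothing is hidden.* A reader might infer that the rule conceals drug effects. It does not. SAP 6.7 keeps counts and percentages for every event by arm, so a 3/3/3/3 pattern beside placebo is visible and can be summed. Tier-1 events get intervals whatever their count, and serious events and withdrawals due to adverse events are summarised in their own right. Four cases on placebo or tofacitinib would also trigger tier 2. This stands: only the planned estimate and its interval are missing.

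*The extreme case is rare.* Twelve cases on drug with no interval is possible, but a reader might take it as typical. Given 12 cases at equal rates, it happens in 2.4% of trials. This stands too. The gap matters at roughly 10 cases or fewer.

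*The contrast by true rate flatters pooling.* The 28% versus 89% at a 4% rate keeps the count at 4 while the denominator rises from 42 to 161. Much of the gain therefore comes from lowering the bar from about 10% to 2.5%, and a 3–4% event failing a 10% bar may be what the SAP intends. This stands, and it is why no particular pooled count is urged here.

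*The pooled interval is not sharp.* Placebo has only about 35 subjects. At 4% in both groups the pooled half-width is 1.96 × √(0.0384 × (1/161 + 1/35)) = 7.2 points. The 10% event used for the standard errors would reach tier 2 anyway in 97% of trials, so that comparison shows the value of a pooled column, not the cost of the tier rule. The gain in precision is real but modest.

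Finally, a redaction in SAP 6.7.1 sits directly before the sentence on intervals, and the sponsor's reporting standards and Safety Review Plan are not supplied. A combined column could be specified there.

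**Conclusion.** The point holds as a gap in the visible plan. Tier 2 is decided arm by arm, intervals follow the tier, and no combined PF-06650833 group is listed. For a non-tier-1 event at equal rates, 8 cases on drug leave every dose arm below 4 in about 57% of trials, 10 cases in about 22% and 12 cases in about 2%.

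These figures assume pro rata arms of 42/42/42/35, equal true rates across doses, a threshold counted in subjects, and no trigger from placebo or tofacitinib. If the unprinted unit were percent, 3/42 = 7.1% would already qualify and the result would change.

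The documents do not support the stronger inference that safety signals go unreported or that the tier rule is an error. Nothing contradicts itself, no data go uncollected, and the primary analysis is untouched. This is a cheap improvement in precision and presentation.

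**What to change.** 1. In SAP 3.6 and 6.7, add an all-PF-06650833 column to both sets of safety tables, beside the four dose columns. Where tier-1 and tier-2 differences are shown, give the combined risk difference and 95% interval versus placebo.
2. In SAP 3.6.1, let the combined group also qualify a Preferred Term for tier 2, at a subject count or percentage the sponsor fixes before unblinding. The level is the sponsor's choice, but it adds terms only if set at 12 subjects or fewer (7.5% of 161), because 13 or more cases on drug always put at least 4 in one arm.
3. In the same sentence, state that the existing 4 means subjects.

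If the redacted text or the sponsor's standards already provide a combined column, a cross-reference in 3.6 and 6.7 would settle item 1.

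The cost is a sentence or two and one column per table set, with no new data. There will be a few more tier-2 rows. The pooled estimate averages over a 20-fold dose range and can dilute a toxicity confined to the higher doses, so it supplements the by-dose comparisons and must not replace them.

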3.6.2. Laboratory Data

Laboratory data will be listed and summarized by treatment in accordance with the Pfizer reporting standards.

3.6.3. Vital Signs

Absolute values and changes from baseline in systolic and diastolic blood pressure, respiratory rate, pulse rate and temperature will be summarized by treatment and visit, according to Pfizer reporting standards.

3.6.4. Electrocardiogram (ECG)

Categorical summary tables will be summarized by treatment and visit using Pfizer reporting standards. A listing of ECG comments on findings and normal/abnormal results will be provided.

4. ANALYSIS SETS

4.1. Intent-to-Treat Analysis Set

An intent-to-treat (ITT) analysis set will include all subjects who were randomized to the study and received at least one dose of the randomized investigational drug (PF-06650833, tofacitinib, or placebo).

4.2. Safety Analysis Set

The safety (SAF) analysis set is defined as those subjects who received at least one dose of the investigational drug.

4.3. Other Analysis Sets

Per-protocol (PP) analysis set is defined as a subset of ITT who had no major protocol violations. The subjects excluded from the PP will be determined and documented before the study is unblinded.

5. GENERAL METHODOLOGY AND CONVENTIONS

Final analyses will occur after database lock after Last Subject Last Visit (LSLV).

5.1. Hypotheses and Decision Rules

For any given active arm, the null hypothesis that the distributions of SDAI change from baseline at Week 12 are the same for the active and the placebo arms will be tested using Bayesian framework outlined in the [Appendix 4](#). The separation from the placebo will be judged based on the probability of the posterior distribution of the treatment effect (Δ^*) being greater than zero.

5.2. General Methods

In general, number and percent will be presented for binary variables. Number, mean, standard deviation (or standard error of the mean), median, minimum, and maximum will be presented for continuous variables. In addition, graphics may be used to present the data.

5.2.1. Analyses for Binary Data

The normal approximation for the difference in binomial proportions will be used to assess the difference between active and placebo.

The normal-approximation to the test statistic for the difference in binomial random variables is calculated as

$$Z_i = \frac{\hat{p}_i - \hat{p}_c}{\sqrt{\frac{\hat{p}_i(1-\hat{p}_i)}{n_i} + \frac{\hat{p}_c(1-\hat{p}_c)}{n_c}}}$$

where \hat{p} refers to the relative frequency, n to sample size, the subscript c refers to the control group (eg, placebo) and the subscript i refers to the active group.

Two-sided 95% confidence intervals are formed by:

$$(\hat{p}_i - \hat{p}_c) \pm Z_{0.975} \sqrt{\frac{\hat{p}_i(1-\hat{p}_i)}{n_i} + \frac{\hat{p}_c(1-\hat{p}_c)}{n_c}}$$

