9.1. Sample Size Determination

The primary endpoint of the study will be the change from baseline in the simplified disease activity index (SDAI) at 12 weeks. The study will enroll approximately 198 completers allocated as follows:

PF-06650833 400 mg	PF-06650833 200 mg	PF-06650833 60 mg	PF-06650833 20 mg	Tofacitinib 5 mg BID	Placebo
36	36	36	30	30	30

Assuming a 15% dropout rate the study will enroll approximately 230 subjects. Since the use of tofacitinib in this study may be not be acceptable by regulatory authorities/ethics committess in all countries, achieving full randomization into the tofacitinib arm may prove logistically challenging. Since the tofacitinib arm is serving as an active control for the study, enrollment of approximately 20-30 subjects into that arm will be acceptable.

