5.3.1. Binary Endpoint

For the binary response endpoints (eg, SDAI remission rates), subjects with missing values will be handled by:

- non-responder imputation (NRI) method, ie, setting any missing values to be non-responsive (0).
- will be used as observed (ie, excluding any missing values from analysis).

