6.2. Secondary Endpoint(s)

6.2.1. SDAI

Analysis of number of subjects with SDAI remission ($SDAI \leq 3.3$) and SDAI low disease activity ($SDAI \leq 11$) at Weeks 4, 8, and 12:

- ITT population set;
- Missing data imputation:
 - Observed;
 - NRI.
- Normal approximation.

Analysis of change from baseline in SDAI at Weeks 4, 8, and 12:

- ITT population set;

- Missing data imputation – none (Observed);
- MMRM.

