6.2.2. DAS

For DAS28-3 (ESR), DAS28-3 (CRP), DAS28 -4 (ESR), and DAS28-4 (CRP), analysis of number of subjects with DAS28 remission (DAS <2.6) and DAS28 low disease activity (DAS28 <3.2) at Weeks 4, 8, and 12:

- ITT population set;
- Missing data imputation:
 - Observed;
 - NRI.
- Normal approximation.

Analysis of change from baseline in DAS28-3 (ESR), DAS28-3 (CRP), DAS28 -4 (ESR), and DAS28-4 (CRP) at Weeks 4, 8, and 12:

- ITT population set;
- Missing data imputation – none (Observed);
- MMRM.

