9. APPENDICES

Appendix 1: Summary of Efficacy Analyses

Primary Efficacy Endpoint	Statistical Method	Missing Data
Change from baseline in SDAI at Week 12	ANCOVA with baseline SDAI as a covariate	Observed
Change from baseline in SDAI at Week 12	ANCOVA with baseline SDAI as a covariate	LOCF
Change from baseline in SDAI at Week 12	ANCOVA with baseline SDAI and anti-TNF use as covariates	Observed
Change from baseline in SDAI at Week 12	ANCOVA with baseline SDAI and anti-TNF use as covariates	LOCF
Change from baseline in SDAI at Week 12	Bayesian analysis of posterior distributions of the SDAI scores and placebo adjusted change from baseline	-

Note: Populations (ITT, PP); Treatment Groups (PF-06650833, placebo)

Secondary Efficacy Endpoints	Statistical Method	Missing Data
SDAI remission and low disease activity scale at Weeks 4, 8, and 12	Normal approximation	Observed
SDAI remission and low disease activity scale at Weeks 4, 8, and 12	Normal approximation	NRI
DAS28-3 (ESR), DAS28-3 (CRP), DAS28 -4 (ESR), and DAS28-4 (CRP) remission and low disease activity scale at Weeks 4, 8, and 12	Normal approximation	Observed
DAS28-3 (ESR), DAS28-3 (CRP), DAS28 -4 (ESR), and DAS28-4 (CRP) remission and low disease activity scale at Weeks 4, 8, and 12	Normal approximation	NRI
Change from baseline in SDAI at Weeks 4, 8, and 12	MMRM	Observed

090177e190fc4501\Approved\Approved On: 27-May-2019 06:05 (GMT)

Secondary Efficacy Endpoints	Statistical Method	Missing Data
Change from baseline in DAS28 (eg, DAS28-3 (ESR), DAS28-3 (CRP), DAS28 -4 (ESR), and DAS28-4 (CRP)) at Weeks 4, 8, and 12	MMRM	Observed
ACR20, ACR50, and ACR70 at Weeks 4, 8, and 12	Normal approximation	Observed
ACR20, ACR50, and ACR70 at Weeks 4, 8, and 12	Normal approximation	NRI
Change from baseline in hsCRP at Weeks 4, 8, and 12	MMRM	Observed
Change from baseline in in the Tender/Painful and Swollen Joint Count (28) at Weeks 4, 8, and 12	MMRM	Observed
Change from baseline in PhGA of Arthritis at Weeks 4, 8, and 12	MMRM	Observed

Note: Populations (ITT); Treatment Groups (PF-06650833 and placebo)

090177e190fc4501\Approved\Approved On: 27-May-2019 06:05 (GMT)

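### The unpooled Wald statistic and interval fixed for all responder and remission endpoints give no usable error bar when neither arm has a responder, and undercover at low unequal rates

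*SAP*

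**What the plan says.** SAP 5.2.1 fixes one method for binary data: "The normal approximation for the difference in binomial proportions will be used to assess the difference between active and placebo". The printed denominator is the unpooled standard error, built from each arm's own observed proportion. The interval uses the same standard error: "Two-sided 95% confidence intervals are formed by" the observed difference plus or minus the 0.975 normal quantile times that error.

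SAP 6.2.1 to 6.2.3 and Appendix 1 assign this method to every visible binary efficacy endpoint:

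- SDAI remission (SDAI of 3.3 or less) and low disease activity: "Analysis of number of subjects with SDAI remission".
- The same two states for four DAS28 versions: "analysis of number of subjects with DAS28 remission (DAS <2.6) and DAS28 low disease activity (DAS28 <3.2) at Weeks 4, 8, and 12".
- The ACR responder rates: "ACR20, ACR50, and ACR70 at Weeks 4, 8, and 12".

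Each is analysed twice, once on observed values and once with missing values counted as non-response (SAP 5.3.1). Tofacitinib is summarised descriptively only (SAP 3), so the comparisons are the four PF-06650833 doses against placebo.

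On size, Protocol 9.1 says "The study will enroll approximately 198 completers allocated as follows": 36, 36, 36 and 30 on PF-06650833, 30 on tofacitinib and 30 on placebo. It adds: "Assuming a 15% dropout rate the study will enroll approximately 230 subjects". The SAP gives no exact, score or continuity-corrected alternative and no rule for cells with no events.

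**The concern.** The Wald standard error estimates each arm's variance from that arm's observed proportion. An arm with no responders is therefore credited with no variance. If both arms are empty, nothing is left to divide by. With a placebo arm of about 30, a strict endpoint such as SDAI remission at Week 4 could produce such cells, and counting missing values as non-response pushes the counts lower still.

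At stake is the accuracy of the error bars in the responder and remission tables. A [0, 0] interval says the difference is known exactly when it is not. With a few responders on active drug and none on placebo, the interval ignores all uncertainty about placebo. Without a rule set in advance, the sponsor would have to choose how to present these cells after seeing them.

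**Working it through.** **Arm sizes.** Inputs are 198 completers and 15% dropout (Protocol 9.1). 198/0.85 = 232.9 and 198 x 1.15 = 227.7, so the plan's figure of about 230 is reproduced. Scaling the arms: 230 x 36/198 = 41.8 and 230 x 30/198 = 34.8. The pairs (active, placebo) are therefore 36/30 and 30/30 for completers, and 42/35 and 35/35 for the randomised and dosed set.

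**Number of comparisons.** 2 SDAI + 8 DAS28 + 3 ACR = 13 endpoints; 13 x 3 visits x 4 doses x 2 missing-data rules = 312 intervals.

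**Formula (SAP 5.2.1).** SE = sqrt[p_i(1-p_i)/n_i + p_c(1-p_c)/n_c]; Z = (p_i - p_c)/SE; interval = difference +/- 1.96 SE. SE is zero only if each arm is at 0% or 100%. A single responder restores it: 1/36 against 0/30 gives -2.6% to 8.1%.

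**Chance that both arms are empty.** With a common true rate p this is (1-p)^(n_i+n_c). All response rates here are assumptions.

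| True rate, both arms | 36/30 | 30/30 | 42/35 | 35/35 |
|---|---|---|---|---|
| 1% | 52% | 55% | 46% | 49% |
| 2% | 26% | 30% | 21% | 24% |
| 5% | 3.4% | 4.6% | 1.9% | 2.8% |
| 10% | 0.1% | 0.2% | <0.1% | 0.1% |

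For example, 0.98^66 = 0.264 and 0.98^77 = 0.211.

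**Coverage and rejection.** Every pair of counts was enumerated with its binomial probability.

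| Active vs placebo rate | 36/30 | 30/30 | 42/35 | 35/35 |
|---|---|---|---|---|
| 5% vs 2%, coverage | 89% | 85% | 87% | 83% |
| 5% vs 1%, coverage | 84% | 78% | 88% | 83% |

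- *Direction of the misses.* At 36/30 and 5% vs 2%, 10.6% of intervals lie wholly below the true difference and 0.5% above it. Most of the former are empty-empty cells: 0.95^36 x 0.98^30 = 0.158 x 0.545 = 8.6%. At 5% vs 1% the split is 15.8% below and 0.6% above.
- *Equal rates of 1-5%.* Coverage is 96-100%, and the test rejects in 0.03-4.1% of trials at nominal 5%.
- *Equal rates of 10-30%.* Rejection is 5.3-6.0%.
- *Equal rates of 40-50%.* Rejection is 5.2-7.2%; the maximum is at 35/35 and 50%.

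**Two cells by hand, against the Miettinen-Nurminen (MN) score method.** MN uses Z(d) = (p_i - p_c - d)/sqrt{[r_i(1-r_i)/n_i + r_c(1-r_c)/n_c] x N/(N-1)}, where N = n_i + n_c and r_i, r_c are the maximum-likelihood rates constrained to differ by d. The limits are the values of d with Z(d) = +/-1.96.

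- *0/36 vs 0/30.* Wald gives [0, 0]. For MN, one restricted rate is |d| and the other 0, so each limit is 3.841k/(1 + 3.841k). The upper limit has k = (66/65)/36 = 0.0282, giving 9.8%. The lower has k = (66/65)/30 = 0.0338, giving -11.5%. Newcombe's score interval is -11.4% to 9.6%.
- *4/36 vs 0/30.* Wald: SE = sqrt(0.1111 x 0.8889/36) = 0.0524, Z = 2.12, p = 0.034, interval 0.8% to 21.4%. MN at d = 0: pooled rate 4/66 = 0.0606, SE = sqrt[0.0606 x 0.9394 x (1/36 + 1/30) x 66/65] = 0.0594, Z = 1.87, p = 0.06. Fisher's exact p is 0.12, and Newcombe gives -2.1% to 25.3%.

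**The case against.** Several stronger readings are tempting, and the documents do not support them.

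- *The method breaks down whenever few patients respond.* It does not. Both arms must be empty (or each at 0% or 100%), and at rates of 10% or more that is negligible.
- *It manufactures false positives in rare endpoints.* The 4/36 against 0/30 example invites this, but at equal rates of 5% or less the test rejects less often than 5%. At least 4/36 together with 0/30 has probability of only 0.3% (2% in both arms) to 2.2% (5% in both arms). Fisher's p is also a conservative yardstick. At low unequal rates the dominant error is an interval that understates a real benefit.
- *Empty cells could not be reported.* SAP 5.2 calls for number and percent, so 0/36 and 0/30 would appear. Only Z and the interval fail.
- *A trial conclusion is at risk.* The decision rule (SAP 5.1), primary analysis (SAP 6.1.1) and futility rule (SAP 7) all rest on the Bayesian analysis of SDAI change. The Hochberg adjustment in Protocol 9.2 concerns pairwise ANCOVA comparisons. The binary endpoints are secondary and carry no success criterion.

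All four objections stand and limit the point. They do not remove it: the formula is explicit, it applies to every visible binary efficacy comparison, and no fallback is given. It is also fair that a score method costs apparent power at low rates and can itself overcover: in the six settings 5% vs 2% and 5% vs 1% at 36/30, 30/30 and 42/35, Newcombe covers 99% or more.

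**Conclusion.** The point holds as a minor one about error bars. At 30 to 42 patients per arm, the SAP's interval carries no information when neither arm has a responder, and it covers 78-89% instead of 95% at 5% against 1-2%. At equal rates of 10-30% the shortfall is about one point or less. The largest shortfall seen at equal rates was 2.2 points, at 50% with 35 per arm.

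The size depends on response rates that the documents do not give. If strict remission runs at 1-3%, the empty-cell problem will be common; if every endpoint runs at 10% or more, it will hardly occur. The enumeration takes arm sizes as planned and patients as independent. Redacted sections could not be checked.

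**What to change.** In SAP 5.2.1 replace the Wald statistic and interval with one pre-specified score method for the risk difference: the Miettinen-Nurminen interval with its matching score p-value. Apply it to all binary endpoints in SAP 6.2.1 to 6.2.3 and Appendix 1, whatever the counts, with no switch of test triggered by the data. One convention should be written down: when neither arm has a responder the score statistic at zero difference is also 0/0, so set p to 1 and report the interval, which remains defined.

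The cost is a paragraph of SAP text and a standard procedure option, plus wider intervals and fewer nominally significant results at low rates. At 15% against 5% with 36/30, the chance of excluding zero falls from about 30% under Wald to about 20% with a Newcombe score interval. The same enumeration with Miettinen-Nurminen gives about 26%. That loss should be stated when the change is made.

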9.4. Randomization

The indicator of prior exposure to anti-TNF treatment will be used as a stratification variable for randomization. The randomization will be stratified with respect to this variable to have equal balance on enrolment of TNF naïve (or TNF exposed) subjects across all arms.

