5.2.2. Analyses for Continuous Data

Mixed Effect Model Repeat Measurement (MMRM) for Longitudinal Continuous Data:

The fixed effects of treatment, visit, and treatment-by-visit interaction will be included, along with patient as a random effect. Unstructured covariance matrix will be assumed.

When modeling the change from baseline values, the variable of visit will start with the first post-baseline visit, and the actual baseline value will be included as a covariate. At each visit, estimates of mean values and the mean differences between the active treated group and the placebo group will be derived from the model. The corresponding p-values, standard errors and 95% confidence intervals will also be derived from the model.

Below is an example of potential statistical analysis system (SAS) code:

```
PROC MIXED DATA=XXX;  
  CLASS SUBJID TREATMENT VISIT;  
  MODEL CHGBASE=TREATMENT VISIT TREATMENT*VISIT BASE/ALPHA=0.05 DDFM=KR;  
  REPEATED VISIT/SUBJECT=SUBJID TYPE=UN;  
  LSMEANS TREATMENT*VISIT/ALPHA=0.05 CL DIFF;  
RUN;
```

Analysis of Covariance (ANCOVA) for Non-longitudinal Continuous Data:

The non-longitudinal continuous data will be analyzed by ANCOVA with treatment as the factor. When modelling change from baseline values, the actual baseline value will be included as a covariate. Active dose group will be contrasted versus placebo.

Below is an example of potential SAS code:

```
PROC MIXED DATA=XXX;  
  CLASS TREATMENT;  
  MODEL CHGBASE=TREATMENT BASE/ALPHA=0.05;  
  LSMEANS TREATMENT/ALPHA=0.05 CL PDIFF;  
RUN;
```

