6.1.2. Sensitivity/Robustness Analyses

There are 3 sets of analyses.

Set 1:

The sensitivity analysis will be based sensitivity prior models on the Bayesian analysis outlined in [Appendix 4](#). The Bayesian analysis will be based on ITT population set.

Set 2:

- Population set
 - ITT;
 - PP.
- Missing data imputation
 - Observed;
 - LOCF.
- ANCOVA (see [Section 5.2.2](#))
 - Baseline SDAI as a covariate;
 - Baseline SDAI and previous anti-TNF use as covariates.

Set 3:

- Population set:
 - ITT;
 - PP.
- Missing data imputation – none (Observed);
- MMRM (see [Section 5.2.2](#)) for analysis of change from baseline in SDAI at Weeks 4, 8, and 12:
 - Baseline SDAI as a covariate;
 - Baseline SDAI and previous anti-TNF use as covariates.

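### Low-disease-activity rates on SDAI and DAS28 are compared as crude proportions, giving up a modest amount of precision that baseline score and anti-TNF stratum could recover

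*SAP*

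**What the plan says.** SAP 5.2.1 gives a single method for binary data: "The normal approximation for the difference in binomial proportions will be used to assess the difference between active and placebo". The test statistic is a Wald Z with unpooled variance. The interval follows the same formula ("Two-sided 95% confidence intervals are formed by" the difference plus or minus the normal quantile times that standard error). Nothing in the section refers to baseline or to a stratum.

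SAP 6.2.1 to 6.2.3 and Appendix 1 assign this method to every visible binary efficacy endpoint, both as observed and with non-responder imputation (NRI):
- SAP 6.2.1, opening "Analysis of number of subjects with SDAI remission", covers SDAI remission (3.3 or below) and SDAI low disease activity (11 or below).
- SAP 6.2.2 covers DAS28 remission (below 2.6) and low disease activity (below 3.2) for four DAS28 versions.
- Appendix 1 lists "ACR20, ACR50, and ACR70 at Weeks 4, 8, and 12".

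The continuous models differ. For change from baseline, SAP 5.2.2 says that "the actual baseline value will be included as a covariate", in both the MMRM and the ANCOVA.

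On the stratum, Protocol 9.4 says: "The indicator of prior exposure to anti-TNF treatment will be used as a stratification variable for randomization". The SAP uses anti-TNF exposure as a covariate only in sensitivity Sets 2 and 3 for the primary endpoint ("Baseline SDAI and previous anti-TNF use as covariates", SAP 6.1.2), and descriptively in the subset summaries of SAP 6.5. Protocol 9.2.1 foresees discrete modelling for secondary endpoints in general terms but names no model.

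**The concern.** SDAI at or below 11 and DAS28 below 3.2 are fixed targets. A patient who starts lower has less far to go, so baseline score should predict the outcome, and a predictive baseline covariate narrows the interval for a treatment difference. The SAP uses this for changes in SDAI and DAS28 but not for threshold endpoints built from the same scores.

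With roughly 35 to 42 patients per arm, intervals on these differences are wide. What is at stake is interval width and the size of chance movements in secondary estimates. Validity is not at stake.

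**Working it through.** **1. Sample size, from Protocol 9.1.** The arms are 36, 36, 36, 30, 30 and 30, summing to 198 completers. At 15% dropout, 198/0.85 = 233 (or 198 × 1.15 = 228), against the stated figure of about 230, so the plan's figure reproduces. Per arm, 30/0.85 ≈ 35 on placebo and 36/0.85 ≈ 42 on each of the three higher doses. NRI keeps dropouts in the denominator, so 35 v 42 is the relevant comparison.

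**2. Assumptions, because the documents give no figures.** Low-disease-activity rates are 15% v 35% or 20% v 45%. The correlation between baseline and the Week 12 score underlying the threshold is 0.2 to 0.6.

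**3. Crude standard error, by the SAP 5.2.1 formula.**
- 15% v 35%: √(0.15×0.85/35 + 0.35×0.65/42) = 0.0952; 95% half-width 1.96 × 0.0952 = 18.7 points.
- 20% v 45%: √(0.20×0.80/35 + 0.45×0.55/42) = 0.1023; half-width 20.1 points.

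**4. Large-sample gain.** The adjusted variance is about (1 − R²) times the crude variance. R² is the variance of P(response | baseline) divided by p(1 − p). With a normal latent score, P(response | x) = Φ((Φ⁻¹(p) − ρx)/√(1 − ρ²)).

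| Response rate p | ρ = 0.2 | 0.3 | 0.5 | 0.6 |
|---|---|---|---|---|
| 0.1 | 0.014 | 0.033 | 0.104 | 0.162 |
| 0.2 | 0.020 | 0.045 | 0.134 | 0.200 |
| 0.3 | 0.023 | 0.052 | 0.150 | 0.220 |

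The anti-TNF stratum adds little. With a 50:50 split and a 10-point difference in rates between strata, R² = 0.10²/4/(p(1 − p)), which is 0.012 at p = 0.3 and 0.028 at p = 0.1.

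**5. Simulation at 35 v 42.** The crude difference was compared with a standardised risk difference from a logistic model, in runs of 5,000 to 10,000 trials per setting. Some runs adjusted for baseline alone, others for baseline and anti-TNF. Variance reductions were:
- ρ = 0.2 to 0.3: about 0–4%
- ρ = 0.5: 10–12%
- ρ = 0.6: 17–20%

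These sit slightly below the R² values, as expected once coefficients are estimated in small arms. Both estimators were essentially unbiased. Shorter runs are unreliable: repeated runs of 1,500 trials at ρ = 0.6 ranged from 15% to 22%.

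**6. What this means.** At ρ = 0.5 and 15% v 35%, a 10% reduction narrows the half-width from 18.7 to 18.7 × √0.90 = 17.7 points. In patient numbers, 10–12% is worth 1/0.90 to 1/0.88, or about 11–14% more per arm. If baseline SDAI has SD 12 (assumed), the standard error of a baseline difference is 12 × √(1/35 + 1/42) = 2.7 points. At ρ = 0.5, an imbalance of one such standard error moves the crude difference by 3.2–3.7 percentage points and the adjusted one by about 0.1.

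**7. Rare outcomes.** At an assumed 2% v 8%, placebo has no responder with probability 0.98³⁵ = 0.49, and at least one of the two arms has none in about 51% of trials. The logistic model could not be used in about 57% of simulated trials. Where it could, it gained nothing; in one run its variance was about 8% larger.

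**The case against.** The case for leaving SAP 5.2.1 alone is reasonable.

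- **The crude difference is unbiased under randomisation, and its standard error already allows for chance imbalance.** This stands. A reader might infer from step 6 that the planned analysis is biased or invalid. It is not; ignoring the stratum makes the interval at most slightly conservative.
- **The gain does not extend to all binary endpoints.** This stands. A reader might conclude that every responder and remission comparison loses precision at no cost. ACR20/50/70 measure change relative to baseline, so their dependence on starting level may be near zero, and rare remission outcomes often cannot support the model.
- **The contrast with the continuous models fails for anti-TNF.** This stands. The primary Bayesian model in SAP Appendix 4 and the secondary MMRMs also omit it. The inconsistency concerns baseline only. The stratum is worth including because it reflects the randomisation, with little precision of its own.
- **No decision depends on these endpoints.** The rules in SAP 5.1 and Section 7 use SDAI change, and baseline-adjusted MMRMs on SDAI and DAS28 are already planned. This limits the importance of the point but does not remove it, since the low-disease-activity rates will still be reported with intervals.
- **A fallback without a threshold would let the estimator depend on the data.** This stands and is met by fixing the threshold in advance.

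**Conclusion.** The point holds for SDAI and DAS28 low disease activity only, as a loss of precision in a valid analysis. Its size rests on assumed rates and an assumed baseline correlation: negligible if the correlation is 0.2–0.3, worth having at 0.5 or above. Even then, about one percentage point off a half-width near 19 is unlikely to change how a phase 2 result is read. It is an inexpensive improvement, not an error that has to be corrected.

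**What to change.** Amend SAP 5.2.1 before unblinding, for SDAI and each DAS28 low-disease-activity endpoint:

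- **Main NRI estimate:** the standardised (g-computation) risk difference for each PF-06650833 dose against placebo, from a logistic model with treatment, the baseline value of the same score and prior anti-TNF exposure, with a delta-method or bootstrap 95% interval.
- **Supportive line:** the crude difference as now specified.
- **Fallback:** the crude difference becomes the main estimate when responders fall below a fixed minimum count. The SAP should state that number and apply it uniformly to all arms for a given endpoint and visit.
- **No change** to rare remission endpoints or ACR20/50/70.

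SAP Appendix 1 needs matching rows. The cost is a paragraph of text and a small modelling and programming burden; no new data, visits or patients are needed. If the baseline correlation proves weak, the gain will be small.
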